1.2. RATIONALE FOR CURRENT STUDY

More widespread use of ultrasound for examining the iliac veins would be beneficial as it may avoid the need to expose patients to the invasive procedures requiring radiation and contrast agents that are necessary for venography and IVUS. Previous studies examining duplex ultrasound and iliac veins, as mentioned above, have examined the use of velocity ratios, interrogation of the CFV and examination of phasicity but have not investigated using ultrasound to measure the absolute diameter of the CIV. There is currently no definitive diameter that the CIV can be considered compressed or not compressed. All of the previous studies used symptomatic patients only and so it cannot be assumed that the results would correlate in asymptomatic patients. Also, it is known that ultrasound is highly operator dependent but none of the previous studies examined the impact of this on measuring the CIV diameter. Therefore, further work needs to be carried out to assess the use of ultrasound for imaging the left CIV and aiding MTS diagnosis.

The principle research question is whether duplex ultrasound could be used to image the left CIV and investigate diameter ranges that can help in the diagnosis of MTS. The first objective is to use duplex ultrasound to image the left CIV in a cohort of patients referred to the vascular ultrasound clinic. The second objective is to determine inter- and intra-observer variation of the diameter measurement of the left CIV using duplex ultrasound. The hypothesis is that ultrasound can be used to image left CIV compression and the measurements obtained during the examination are highly reproducible both within an operator and between operators.

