2. STUDY OBJECTIVES

The primary objective of this study is to investigate diameter variation of the left CIV based on posture in adults referred to the vascular ultrasound department, using duplex ultrasound.

The secondary objective of this study is to determine inter- and intra-observer variation of the diameter measurement of the left CIV using duplex ultrasound, in adults referred to the vascular ultrasound department.

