3. STUDY DESIGN

The study will be a feasibility/pilot study lasting approximately six months, recruiting 40 patients from the vascular ultrasound department at Imperial College Healthcare NHS Trust. 20 patients will be symptomatic for lower limb venous disease and 20 patients will be asymptomatic. The following outlines the timeline of events for the patients recruited onto the study.

OUTPATIENT APPOINTMENT

At their outpatient appointment patients who may be eligible to take part in the study will be identified and approached. Patient notes and GP referral letters will be read prior to seeing the patient in the outpatient appointment, to identify suitable participants. Suitable participants will be those that will be requiring a vascular ultrasound scan in the vascular ultrasound department. The study will be explained and if the patient gives verbal consent to receiving study information material, then this will be given to the patient for consideration. They will be told that formal consent will be taken at their scan appointment if they agree to partake in the study and that if they choose not to partake this will not affect their usual clinical care. Participants will be given up to six weeks to decide if they would like to take part.

TELEPHONE CALL

Patients will be contacted two weeks after their outpatient appointment to enquire as to whether they would like to take part in the study. Those that decline will have their scan request form passed on to the department receptionist for booking in the usual way. Those that would like to take part in the study will have a date and time arranged to come to the department to have their scan as part of the study, followed by the scan requested by the clinical team. The study scan and the routine scan will be made on the same day to avoid the patient having to come to the hospital multiple times. Some patients from the symptomatic group may have been referred for this type of scan.

[figure not shown]
ULTRASOUND SCAN APPOINTMENT

Order of events at the scan appointment will be as follows;

[figure not shown]
- Eligibility check and formal consent - 5 minutes
- Recording of demographic details and medical history - 5 minutes
- The patient will have their routine scan performed as requested by the referring clinician - Between 30 and 90 minutes, dependent on the scan type requested.

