- A clinical vascular scientist will perform the study ultrasound scan and take three readings of the left CIV with the patient lying flat and three readings of the left CIV with the patient at a 45 degree angle on a tilted examination couch - 10 minutes
- Two further clinical vascular scientists will perform the same study scan and take the same readings - 20 minutes
- Patient will be thanked for their time and a routine follow up appointment will be made with the referring clinician.

The below flow chart illustrates this order of procedures:

Prior to the ultrasound scan appointment:

During the ultrasound scan appointment:

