3.1. STUDY OUTCOME MEASURES

The primary outcome measure is the diameter variation ranges of the left CIV in adults referred to the vascular ultrasound department.

The secondary outcome measure is the inter- and intra-operator variation of the diameter measurement of the left CIV using duplex ultrasound, in adult patients referred to the vascular ultrasound department.

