7. STATISTICS AND DATA ANALYSIS

The sample size has been calculated using a sample size calculator assuming a prevalence of 2%, confidence level of 95% and margin of error of 5%. This calculation gives a sample size of 31. This sample size is in line with a previous study by Mousa et al. (2016) which had a sample size of 36.

A one-way ancova test will be performed to assess the difference in iliac vein diameter between the two groups. An intraclass correlation coefficient will be used to measure intra- and inter-observer reliability. Support will be provided from the Imperial Statistics Services during the analysis phase.

Statistics and data analysis aspects of the study have been reviewed by [name], the academic supervisor at Manchester Metropolitan University.

Data and all appropriate documentation will be stored for a minimum of 10 years after the completion of the study, including the follow-up period.

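### Posture order is listed as flat then 45 degrees for every operator and is not balanced, so an order effect that recurs within operators could not be separated from the primary posture difference

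*Combined protocol and SAP*

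**What the plan says.** Section 2: "The primary objective of this study is to investigate diameter variation of the left CIV based on posture in adults". Section 3.1 words the outcome more loosely and leaves posture out: "The primary outcome measure is the diameter variation ranges of the left CIV in adults referred to the vascular ultrasound department".

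Section 3 opens the appointment list with "Order of events at the scan appointment will be as follows". In that list the first operator is to "take three readings of the left CIV with the patient lying flat and three readings of the left CIV with the patient" at 45 degrees on a tilted couch, and then "Two further clinical vascular scientists will perform the same study scan and take the same readings". No other posture order is given, and nothing is said about varying or noting the order.

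Section 7 plans a one-way ANCOVA between the symptomatic and asymptomatic groups, and "An intraclass correlation coefficient will be used to measure intra- and inter-observer reliability". It has no posture comparison and no order term. Section 1.2 states the hypothesis that "the measurements obtained during the examination are highly reproducible both within an operator and between operators".

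The telephone-call part of section 3 says that patients come "to have their scan as part of the study, followed by the scan requested by the clinical team". The appointment list in the same section puts the routine scan before the study scan.

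**The concern.** In a within-patient comparison of two postures, the order of the postures is part of the design. If flat always comes first, anything that differs between an operator's first and second set of readings is counted as posture. A larger sample does not help, because the bias is the same in every patient. Recording the order does not help either if everyone has the same one. The order has to be varied before scanning starts.

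What is at stake is the flat-to-tilt difference, which is the quantity that the primary objective asks for. A secondary matter is the reliability coefficients: the text does not say whether each of the three readings needs the vein to be found again, or whether later operators are kept from seeing earlier values.

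**Working it through.** **Inputs from the protocol.** 40 patients, 20 per group; 3 operators; 2 postures; 3 readings per posture, so 3 × 2 × 3 = 18 readings per patient; 10 + 20 = 30 minutes allotted. The protocol gives no SD, order effect or posture test, so the millimetre values below are assumptions. The one calculated figure in section 7, the sample size, reproduces (1.96² × 0.02 × 0.98 / 0.05² = 30.12, rounded up to 31) but does not bear on this point.

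**1. Can posture and position be separated?** Take a model with 40 patient terms, 2 operator terms, posture, and first/second position within operator: 44 columns.
- Listed order: posture and position have correlation 1.0 and the matrix has rank 43 of 44. The posture effect cannot be estimated apart from position.
- Half the patients flat-first and half tilt-first: correlation 0, rank 44 of 44. Both effects can be estimated.

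**2. How large is the bias?** The blocks run F-T-F-T-F-T over the three operators. Bias = mean of the T blocks − mean of the F blocks, with no true posture effect and an assumed effect of 0.5 mm:

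| Pattern | F blocks | T blocks | Bias (mm) |
|---|---|---|---|
| Steady drift from 0 to 0.5 | 0, 0.2, 0.4 | 0.1, 0.3, 0.5 | 0.30 − 0.20 = 0.10 |
| One-off shift after block 1 | 0, 0.5, 0.5 | 0.5, 0.5, 0.5 | 0.50 − 0.33 = 0.17 |
| Recurs within each operator | 0, 0, 0 | 0.5, 0.5, 0.5 | 0.50 |

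Tilt-first patients give −0.10, −0.17 and −0.50, so a balanced list averages to 0 in all three cases. A linear drift term would not rescue the listed order if the operators also came in a fixed order and had their own terms (rank 43 of 44). It could be estimated if operator order varied (44 of 44).

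**3. Illustration only: a paired t test.** None is planned. With n = 40, 39 df, two-sided 5%, no true effect, and an SD of change of 1.0/1.5/2.0 mm (assumed), p < 0.05 would occur in:
- bias 0.10 mm: 9.5%/7.0%/6.1%
- bias 0.17 mm: 17.7%/10.5%/8.1%
- bias 0.25 mm: 33.8%/17.7%/12.0%
- bias 0.50 mm: 86.9%/53.8%/33.8%

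**4. Cost of the order term.** Half-width of the 95% interval at an assumed SD of 1.5 mm: t × 1.5/√40. With 39 df it is 0.4797 mm; with 38 df, 0.4801 mm.

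**5. Secondary: reliability, assumed inputs.** If one operator's repeats share a fraction f of the error variance, the apparent intra-observer ICC is ICC + f(1 − ICC). A true 0.70 then appears as 0.775, 0.85 or 0.925 for f = 0.25, 0.50 or 0.75. If operators 2 and 3 are pulled a fraction w towards the first operator's value, the apparent inter-observer ICC is

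[ICC + (1 − ICC)(2w + w²)/3] / [ICC + (1 − ICC){1 + 2((1 − w)² + w²)}/3].

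For a true 0.70 and w = 0.25 this is 0.756/0.925 = 0.82; for w = 0.10 and 0.50 it is 0.75 and 0.92.

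**The case against.** The strongest reply has four parts.

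- **The only planned diameter test is the between-group ANCOVA.** Both groups follow the same list, so an order effect common to them cancels from that comparison. This stands. The harm is confined to the flat-to-tilt difference, unless the order effect differs between groups.
- **The damaging pattern is a special one.** It must appear between each operator's two blocks, vanish at handover and return. The protocol suggests no mechanism and no size for it. The alternation of postures across operators already dilutes drift and one-off shifts. This also stands, and so the 0.50 mm case and its rejection rates are an assumed upper end. A reader might infer that the posture result is likely to be a false positive. The documents do not support that.
- **The list does not forbid another order, and the form may record it.** Section 8.3 mentions a paper case report form, which is not supplied, and the flow chart is not shown. A reader might infer that order goes unrecorded; all that can be said is that the supplied text does not mention it. The need to vary the order remains.
- **Silence on repeats is not evidence of bias.** Having two further scientists perform the scan implies that each operator scans separately, and nothing says that earlier values are visible. A reader might infer that the ICCs will be inflated. That is possible, but the documents do not show it.

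The study is also a feasibility/pilot study. That limits the weight of the point, although a pilot is a sensible place to settle a scanning procedure.

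**Conclusion.** The point holds in limited form. If the listed order is followed for every patient, a first-versus-second effect that recurs within operators passes in full into the flat-to-tilt difference, and no later analysis can remove it. Steady drift and one-off shifts pass through only in part: one fifth (0.10 of 0.5 mm) and one third (0.17 of 0.5 mm). These fractions follow from the block layout; the 0.5 mm itself is assumed, and whether any order effect exists cannot be learned from the documents.

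This is a cheap improvement to a pilot and not a fatal flaw. The acquisition and concealment of repeat readings is a secondary clarification. The two statements on whether the study scan comes before or after the routine scan do contradict each other. That is a separate matter: both postures are measured within the same study scan, so it does not confound the within-patient posture difference.

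**What to change.** 1. **Order.** Use a pre-printed list with 10 flat-first and 10 tilt-first patients in each group of 20. Keep one posture order per patient across the three operators, and record the order actually used.
2. **Analysis.** Add a posture analysis to section 7: for each patient take mean tilt minus mean flat, and fit it with an order term (40 − 2 = 38 df). State as a limitation that balancing does not remove unequal carry-over between the postures.
3. **Repeat readings (secondary).** Require the vein to be found again for each reading, and use separate forms so that later operators do not see earlier values.
4. **Scan sequence (separate).** Reconcile the two statements in section 3 on whether the study scan precedes or follows the routine scan.

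**Cost.** Items 1 and 2 need a list, a form field and one degree of freedom. Both orders need five couch changes between blocks; tilt-first may need one more at the start if the couch begins flat. Item 3 adds an assumed 15–30 s to each reading, against the 1,800/18 = 100 s now allotted: 18 × 15–30 s = 4.5–9 minutes per appointment, or 3–6 hours over 40 patients. No extra patients or operators are needed.

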1. INTRODUCTION

1.1. BACKGROUND

May Thurner Syndrome (MTS) is a vascular condition whereby the left common iliac vein (CIV) becomes compressed between the right common iliac artery and the spine. This condition is often asymptomatic, however MTS can cause severe left lower limb complications such as swelling, pain, oedema, reflux, varices, skin changes and deep vein thrombosis (DVT). It is thought that approximately 2-3% of lower limb DVT's are caused by MTS, however there is an almost 56% predominance for left sided DVT suggesting this number is underestimated and cases of MTS are regularly missed (Peters et al., 2012). DVT can be a serious medical condition and can go on to cause pulmonary embolism, a sometimes fatal condition if not identified and treated quickly and effectively.

Diagnostic imaging studies such as ultrasonography, venography and intravascular ultrasound (IVUS) are used to evaluate the CIV and identify the site and severity of any narrowing that is present. Duplex ultrasound is often the first line of imaging as it is risk free, cost effective, and accurate at identifying lower limb venous insufficiency. However the location of the iliac veins deep in the abdomen has limited its use for identifying specific features of MTS. It is also highly operator dependent and the results obtained may be dependent on the experience level of the vascular scientist performing the scan. Abdominal ultrasound scans are also always performed with the patient lying completely flat, however this does not reflect the haemodynamic changes that occur within the venous system when a patient is standing. Indirect measurements can be taken to help indicate if there is an iliac vein obstruction, such as interrogation of the common femoral vein (CFV) to assess phasicity and reflux. However, these readings can suggest proximal problems but do not differentiate between compression and thrombus.

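### No step keeps the three operators unaware of symptom group, so a shared expectation could bias the symptomatic versus asymptomatic comparison of left CIV diameter

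*Combined protocol and SAP*

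**What the plan says.** Section 3 (Study Design) sets up two groups: "20 patients will be symptomatic for lower limb venous disease and 20 patients will be asymptomatic". At the appointment the first operator is to "take three readings of the left CIV with the patient lying flat and three readings of the left CIV with the patient at a 45" (the last figure is the tilt of the couch, in degrees), and then "Two further clinical vascular scientists will perform the same study scan and take the same readings". Section 7 plans one between-group test: "A one-way ancova test will be performed to assess the difference in iliac vein diameter between the two groups". It also plans an intraclass correlation coefficient (ICC) for intra- and inter-observer reliability.

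On the measurement itself, section 1.1 says of duplex ultrasound: "It is also highly operator dependent and the results obtained may be dependent on the experience level of the vascular scientist performing the scan". Section 1.2 applies this to the quantity measured here: "it is known that ultrasound is highly operator dependent but none of the previous studies examined the impact of this on measuring the CIV diameter".

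The appointment schedule lists "Recording of demographic details and medical history - 5 minutes" ahead of any scanning, then the routine scan, then the study scan. The telephone-call paragraph of the same section gives the opposite order, with the study scan first and the clinically requested scan after it. That paragraph adds that some symptomatic patients may have been referred for this very type of scan.

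Sections 3, 3.1 and 7 contain nothing on masking operators to group, withholding referral information, or reading coded images off-line. The study code in section 8.3 serves confidentiality; it is not described as masking anyone who scans.

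**The concern.** The section 7 comparison depends on what an operator chooses to image and measure in a deep abdominal vein. An operator who knows that a patient is symptomatic may expect a narrower vein and, without intending to, accept a narrower view. The reverse can happen in an asymptomatic patient.

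The available text leaves three routes by which group can become known: the medical history, the routine scan if it is done first, and the referral itself. It does not say who carries out these steps.

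If operators share the expectation, the usual safeguards do not help. Three readings and three operators reduce random error, but a common shift survives averaging. Because the operators shift together, they still agree, so the ICC gives no warning. A group difference could then reflect the observer, the vein, or both, and the data could not separate them. This matters because section 1.2 hopes for diameter ranges that help diagnose May-Thurner syndrome.

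**Working it through.** **The plan's own figure.** Section 7 gives N = 31 from prevalence 2%, 95% confidence and a 5% margin. 1.96² × 0.02 × 0.98 / 0.05² = 30.12, rounded up to 31. It reproduces, but it concerns the precision of a proportion and has no bearing on this point.

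**Inputs from the documents.** 20 symptomatic and 20 asymptomatic patients (section 3); three operators, each taking three readings per posture (section 3); an ANCOVA of diameter between the groups (section 7), with covariates, significance level and sidedness not stated.

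**Assumptions, because the documents give no figures.**
- Knowing the group shifts the measured diameter by 0.25 to 0.5 mm, in opposite directions in the two groups. The bias in the group difference is then 2 × 0.25 = 0.5 mm to 2 × 0.5 = 1.0 mm.
- The between-patient SD of the analysed diameter is 2, 3 or 4 mm.
- The test is two-sided at 5%, approximated by an unadjusted t-test with 38 degrees of freedom. There is no true difference.

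**Formulas.** SE of the difference = SD × √(2/20). Noncentrality = bias / SE. The false-positive rate is the probability that a noncentral t with 38 df falls outside ±2.024.

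| SD (mm) | SE (mm) | Bias 0.5 mm: bias/SE | False-positive rate | Bias 1.0 mm: bias/SE | False-positive rate |
|---|---|---|---|---|---|
| 2 | 0.63 | 0.79 | 12% | 1.58 | 34% |
| 3 | 0.95 | 0.53 | 8% | 1.05 | 18% |
| 4 | 1.26 | 0.40 | 7% | 0.79 | 12% |

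With no shift the rate is the nominal 5%.

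**Would the ICC reveal it?** Set the total variance to 1, so that the between-patient part is the ICC. A shift of b SD between two equal groups of 20 adds (b²/4) × (40/39) to the between-patient variance and nothing to the disagreement between operators. For b = 0.5 the addition is 0.0641. An assumed ICC of 0.60 becomes (0.60 + 0.0641)/1.0641 = 0.62, and 0.90 becomes (0.90 + 0.0641)/1.0641 = 0.91. At SD 3 mm, where b runs from 0.17 to 0.33, the change is at most about 0.01. The inflation is trivial; what matters is that agreement does not fall.

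**Posture.** Section 2 makes diameter variation by posture the primary objective. If the same shift s enters both postures, the within-patient contrast is (flat + s) − (tilted + s) = flat − tilted, and s cancels. The contrast is biased only if s differs between flat and 45 degrees.

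**Readings available.** All operators: 3 × 3 = 9 per posture. Operators two and three only: 2 × 3 = 6 per posture.

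**The case against.** The strongest reply is that silence about masking is not evidence that operators know the group. The protocol does not say who takes consent and history or who does the routine scan, so operators two and three may already be unaware of it. That stands, but nothing in the available text secures it. The flow charts and the separate appendices could not be examined.

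Several stronger readings are tempting and are not supported:
- A reader might infer that operators place calipers by hand. The protocol says only that they take readings. The argument needs only operator judgement, which sections 1.1 and 1.2 acknowledge.
- A reader might infer that the request form discloses the group. Its content is not described. What section 3 does say is that some symptomatic patients may be referred for this type of scan.
- A reader might take it as settled that the routine scan comes first. Section 3 contradicts itself on this.
- A reader might conclude that the primary objective is compromised. A constant shift cancels in the posture contrast, and neither section 2 nor section 3.1 names a group difference as an objective or outcome.
- A reader might expect the bias to inflate the ICC materially. The calculation shows that it does not.

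It is also fair to say that the group is symptomatic for lower limb venous disease in general, not suspected of left CIV compression. A uniform expectation across all 20 patients, with the opposite expectation in the other 20, is therefore towards the unfavourable end. This is a 40-patient pilot, and both the bias and the SD are assumed.

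**Conclusion.** The point holds for the section 7 group comparison and should be acted on before scanning starts, because bias introduced at image acquisition cannot be removed in analysis. As written, nothing protects that comparison from an expectation shared by operators, and neither the repeat readings nor the ICC would expose one.

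The size is conditional. If the group bias is 0.5 to 1.0 mm, the chance of a false significant difference is between 7% and 34% across SDs of 2 to 4 mm, against a nominal 5%, and the estimated difference is off by the full amount of the bias. The documents show that such bias is possible; they do not show that it will occur or how large it would be. The posture objective is largely unaffected.

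**What to change.** **Section 3, Ultrasound Scan Appointment.** State that operators two and three:
- take no part in consent, history or the routine scan;
- enter only for the study scan, with the study code;
- do not see the request form, the history or the routine scan result;
- do not ask the patient about symptoms;
- record whether they guessed the group.

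**Section 7.** Base the symptomatic versus asymptomatic comparison on the masked readings of operators two and three. Show operator one's readings, or all three operators together, alongside as a sensitivity analysis. Keep all three operators for the ICC.

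**Section 3, scan order.** Reconcile the telephone-call paragraph with the appointment schedule on whether the study scan or the routine scan comes first, since the order affects what operators can know.

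**Cost.** A short conduct instruction and a change to the analysis text, with no extra patients or scans. Because the protocol does not say who performs the routine scan, the site should confirm that two operators can be kept apart from it. Masking will be incomplete when swelling is visible, which should be reported as a limitation together with the recorded guesses. The main group comparison would use six rather than nine readings per posture.
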